The laboratory tests listed in [Table 2](#) will be performed by the central laboratory service provider at Visits 1, 2, 4, 6, 8, 10, 12, 16, 20, EOT and at Week 188 follow-up visit ("complete" lab). At Visits 3, 5, 7, 9, 11, 13, 14, 15, 17, 18, 19, 21, only WBC, serum CRP and serum albumin will be collected ("targeted" lab). A local laboratory may be used for selected tests in exceptional cases. Subjects should be fasting for at least 8 hours prior to the blood sample being taken at the "complete" visits, except for screening (see [Appendix C](#)).

Instructions regarding sample collection, sample handling/processing and sample shipping are provided in the Laboratory Manual in the ISF. For time points of laboratory sampling, see [Appendix C](#).

Laboratory results (i.e., all safety laboratory and clinical laboratory data relevant for current clinical practice) of the subjects will be available in real time to the respective investigator (via laboratory reports) and to the sponsor (via the central laboratory website) and selected abnormal laboratory alerts will be flagged to the site and sent to sponsor in real time.

A clinically relevant value may be either in or outside the reference range. Clinically relevant abnormal laboratory test results must be confirmed using an unscheduled visit laboratory kit and should be repeated until normalization or stabilization or until an alternative explanation has been found. Laboratory abnormalities are considered to be adverse events only if they result in discontinuation from the study, necessitate therapeutic medical intervention, and/or if the investigator considers them to be adverse events.

Table 2. Laboratory Tests

Category	Test Name
Hematology	Hematocrit (Hct) Hemoglobin (Hb) Red Blood Cell Count/Erythrocytes White Blood Cells/Leukocytes Platelet Count/Thrombocytes
Diff. Automatic	Neutrophils (relative count) Eosinophils (relative count) Basophils (relative count) Monocytes (relative count) Lymphocytes (relative count)
Diff. Manual (if Diff Automatic is abnormal)	Neutrophils, bands (Stabs) Neutrophils, polymorphonuclear (PMN) Eosinophils Basophils Monocytes Lymphocytes
Enzymes	AST(GOT) ALT(GPT) Alkaline Phosphatase (AP) Creatine Kinase (CK) CK-MB, only if CK is elevated Gamma-Glutamyl Transferase (GGT/γ-GT)
Electrolytes	Calcium Sodium Potassium Chloride Bicarbonate

Table 2. Laboratory Tests (Continued)

Category	Test Name

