6.1.1.3 Adverse Events of Special Interest

The term adverse events of special interest (AESI) relates to any specific AE that has been identified at the compound level as being of particular concern for prospective safety monitoring and safety assessment within this trial, e.g., the potential for AEs based on knowledge from other compounds in the same class. Ongoing evaluation of adverse events may identify future AESI.

The following are considered as AESI:

Hepatic Injury

A hepatic injury is defined by the following alterations of hepatic laboratory parameters:

- an elevation of aspartate aminotransferase (AST) and/or alanine aminotransferase (ALT) > 3 -fold upper limit of normal (ULN) combined with an elevation of total bilirubin > 2 -fold ULN measured in the same blood draw sample, and/or
- marked peak aminotransferase (ALT, and/or AST) elevations ≥ 10 -fold ULN.

These lab findings constitute a hepatic injury alert and the subjects showing these lab abnormalities need to be followed up according to instructions from the sponsor including completion of the hepatic adverse events form.

In case of clinical symptoms of hepatic injury (icterus, unexplained encephalopathy, unexplained coagulopathy, right upper quadrant abdominal pain, etc.) without lab results (ALT, AST, total bilirubin) available, the investigator should make sure these parameters are analysed, if necessary with an unscheduled blood test. Should the results meet the criteria of hepatic injury alert, investigators are advised to provide a hepatic workup as directed by the Sponsor.

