8.1.6 Safety Analyses

Adverse events will be coded using the Medical Dictionary for Regulatory Activities (MedDRA[®]) coding dictionary. Standard AbbVie summary tables and listings will be produced.

All AEs, SAEs, AEs leading to discontinuation, and pre-specified AEs of special interest will be collected during the study. A treatment-emergent AE (TEAE) is defined as an event with onset or worsening after the first study dose of risankizumab and within 15 weeks (105 days) after the last risankizumab injection. The number and percentages of subjects experiencing TEAE will be tabulated using the MedDRA system organ class and preferred term. Summaries (including percentages and event per 100 subject-years) of SAEs, deaths, AEs leading to discontinuation from the study, and pre-specified AEs of special interest will be provided as well. Mean change in laboratory variables, and vital signs determinations will be summarized. For selected parameters, a listing of all subjects with clinically significant laboratory values and vital sign determinations will be

provided. Shift tables for changes from baseline according to the normal range will also be provided.

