ASI Grouping	Categories (ASI)	Search Criteria	Terms to Display	Include in AE Overview (Y/N)
Possible Drug induced liver injury (DILI)	Possible Drug induced liver injury (DILI)	Broad – Hepatic failure, fibrosis and cirrhosis and other liver damage-related conditions (SMQ 20000013) Broad – Hepatitis, non-infectious (SMQ 20000010) Broad – Cholestasis and jaundice of hepatic origin (SMQ 20000009) Broad – Liver related investigations, signs and symptoms (SMQ 20000008) Narrow – Liver-related coagulation and bleeding disturbances (SMQ 20000015)	PTs	Y

Adverse Event per 100 Patient-Years of Exposure

Adverse events occurring during the entire study will be presented by event rate per 100 patient-year. These will be presented for any TEAEs, serious adverse events, Areas of Special Interest.

AEs per 100 patient-years of exposure is defined as the number of AEs divided by the total exposure in 100 patient-years. Note that one event per preferred term per day per

subject will be counted in the calculation of the number of AEs (i.e., a preferred term will not be counted twice on the same day for the same subject). See the calculation method below.

$$100 \times \frac{\text{Number of TEAEs}}{\text{Total Patient Years}}$$

where total patient years is defined as the sum of the study drug exposure (defined as date of last dose – date of first dose + 105 days (5 half-lives)) of all subjects normalized by 365.25, and rounded to one decimal place.

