A separate listing will be provided that presents all of the subjects and values that are NCI CTCAE toxicity grade 3 or above. For each of these subjects, the whole course of the respective parameter will be listed.

If there are multiple measurements on the same day, the worst value will be used.

Liver Function Tests

Additional summaries will be presented for liver function tests including ALT or serum glutamic-pyruvic transaminase (SGPT), AST or serum glutamic-oxaloacetic transaminase (SGOT), alkaline phosphatase, and total bilirubin. Each laboratory value will be categorized as follows:

- $< 1.5 \times \text{ULN}$
- $\geq 1.5 \times \text{ULN} - < 3.0 \times \text{ULN}$
- $\geq 3.0 \times \text{ULN} - < 5.0 \times \text{ULN}$
- $\geq 5.0 \times \text{ULN} - < 10.0 \times \text{ULN}$
- $\geq 10.0 \times \text{ULN} - < 20.0 \times \text{ULN}$
- $\geq 20.0 \times \text{ULN}$

Shift tables of Baseline to the maximum (relative to the normal range, i.e., the largest multiple relative to the upper limit of normal) values, and from Baseline to final value will be presented using these five categories. A listing of potentially clinically significant liver function laboratory values will be provided. The listing will include all subjects who met any of the following four criteria:

- $\text{ALT} \geq 3 \times \text{ULN}$, or
- $\text{AST} \geq 3 \times \text{ULN}$, or
- Alkaline phosphatase $\geq 1.5 \times \text{ULN}$, or
- Total bilirubin $\geq 2 \times \text{ULN}$.

A listing of possible Hy's Law cases, defined as those who meet all of the following conditions will be provided

- $\text{ALT} > 3 \times \text{ULN}$ or $\text{AST} > 3 \times \text{ULN}$
- Associated with an increase in bilirubin $\geq 2 \times \text{ULN}$

- Alkaline phosphatase $< 2 \times \text{ULN}$

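### No SAP output counts hepatic injury, the protocol's only pre-specified AESI, by the laboratory definition the protocol gives it

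*SAP*

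**What the plan says.** **Definition.** Protocol 6.1.1.3 opens its list with "The following are considered as AESI" and gives a single entry, hepatic injury, while allowing that others may be added. The entry is purely biochemical: "A hepatic injury is defined by the following alterations of hepatic laboratory parameters". Limb 1 is AST and/or ALT above 3×ULN "combined with an elevation of total bilirubin > 2 -fold ULN measured in the same blood draw sample, and/or" limb 2, which is ALT and/or AST at or above 10×ULN. Alkaline phosphatase (ALP) plays no part. The section adds "These lab findings constitute a hepatic injury alert" and requires sponsor-directed follow-up with a hepatic adverse events form. Section 6.1.7 provides a supplemental CRF for hepatic injury.

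**Promise.** Protocol 8.1.6 says that summaries, with percentages and events per 100 subject-years, of "pre-specified AEs of special interest will be provided as well".

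**When a laboratory value is an AE.** Protocol 5.3.1.1: "Laboratory abnormalities are considered to be adverse events only if they result in discontinuation from the study, necessitate therapeutic medical intervention", or if the investigator judges it to be one.

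**SAP, adverse events.** The Areas of Safety Interest table in SAP 11.2.1 builds Possible DILI from five MedDRA queries of reported terms, four broad and one narrow. One of the broad queries is "Liver related investigations, signs and symptoms (SMQ 20000008". This grouping enters the AE overview, gets a by-subject listing and gets a rate per 100 patient-years. The final list of areas is deferred to a product-level safety plan.

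**SAP, laboratory data.** Section 11.3.2 plans:
- shift tables to the maximum for ALT, AST, ALP and bilirubin, each on its own, with categories from 10×ULN upward;
- counts of ALT or AST above 5×ULN, with a Grade 3 or higher listing;
- a liver listing of anyone with ALT or AST ≥3×ULN, ALP ≥1.5×ULN or bilirubin ≥2×ULN;
- a further output: "A listing of possible Hy's Law cases, defined as those who meet all of the following conditions will be provided". The conditions are ALT or AST above 3×ULN, an associated bilirubin ≥2×ULN, and ALP below 2×ULN.

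**Declared changes.** SAP 14.0 is marked as not applicable, and nothing is entered under 14.1.

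**The concern.** The protocol ties a promised incidence and rate to a precise laboratory rule. The SAP gives its liver incidence and rate to something else, a search of AE terms with no laboratory threshold. The one SAP rule that joins aminotransferases to bilirubin differs from the protocol's and produces a listing, not a count.

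A reader of the study report who looks for the AESI figure would therefore find a liver figure with a different meaning. It could be lower, if a qualifying laboratory result was not also reported as an AE. It could be higher, because broad queries admit liver terms that never reached the thresholds. Where the SAP knowingly departs from the protocol elsewhere (NCI CTCAE in place of RCTC for laboratory grading, 11.3.2), it says so and gives a reason. Here it does neither.

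**Working it through.** The documents state no figure to reproduce. The check sets the rules side by side and applies them to constructed laboratory profiles.

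**Rules** (multiples of ULN)

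| | Protocol AESI | SAP Possible DILI | SAP Hy's Law | SAP liver listing |
|---|---|---|---|---|
| Source | Laboratory | Reported AE terms | Laboratory | Laboratory |
| ALT or AST | >3 (limb 1); ≥10 (limb 2) | none | >3 | ≥3 |
| Bilirubin | >2, limb 1 only | none | ≥2 | ≥2 |
| ALP | none | none | <2 | ≥1.5 |
| Same draw | required, limb 1 | not relevant | not stated | not relevant |
| Combination | either limb | any term | all conditions | any one condition |
| Output | n (%) and rate promised | n (%), rate, listing | listing | listing |

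**Profiles** (AST 1×ULN throughout)

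| Profile | AESI | Hy's Law | Liver listing |
|---|---|---|---|
| A: ALT 12, bilirubin 1, ALP 1 | yes | no | yes |
| B: ALT 4, bilirubin 2.5, ALP 2.5, one draw | yes | no | yes |
| C: ALT 4, bilirubin 2.0, ALP 1, one draw | no | yes | yes |
| D: ALT 4 and bilirubin 2.5 in different draws, ALP 1 | no | yes | yes |
| E: ALT 4, bilirubin 2.5, ALP 1, one draw | yes | yes | yes |

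The AESI and Hy's Law rules disagree in both directions. Profile D assumes that an associated bilirubin rise need not come from the same draw; profile C does not depend on that.

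A grid of 8 ALT × 8 AST × 4 bilirubin × 4 ALP values × same or different draw gives 8×8×4×4×2 = 2048 combinations. Of these, 416 met both rules, 640 met the AESI only, 160 met Hy's Law only and 832 met neither (416+640+160+832 = 2048). These are combinations of rules, not expected frequencies.

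**Is any case lost?** No. Limb 1 needs ALT or AST >3 and limb 2 needs ≥10. Either implies ≥3, which alone puts the subject in the liver listing. The grid agrees: no AESI combination fell outside it.

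**Can the AESI count be read from the other tables?**
- *Limb 2, partly.* ALT 12 (profile A) is counted in the ≥10 to <20 shift category and in the >5×ULN table. But ALT and AST are tabulated separately. Two subjects with ALT ≥10 and two with AST ≥10 could be two, three or four people.
- *Limb 1, no.* Profile B has ALT 4, below the >5 cut, and bilirubin 2.5, below that table's >3 cut, so it is not counted there. The shift tables take each analyte's maximum separately, and those maxima may come from different draws.

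**Size of one case.** At the planned 16 subjects, 8 per substudy and 1:1 allocation, an arm within a substudy has 4. One subject is 1/4 = 25%, 1/8 = 12.5% or 1/16 = 6.25%. With no cases, the one-sided 95% upper bound, 1 − 0.05^(1/n), is 52.7% for n=4, 31.2% for n=8 and 17.1% for n=16. The count describes; it cannot exclude much.

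**The case against.** The strongest reply is that the SAP covers the liver thoroughly and that little is at stake. Protocol 6.1.1.3 treats an AESI as a kind of AE and sends qualifying laboratory findings to a hepatic adverse events form. Protocol 8.1.6 does not say that the AESI must be counted from raw laboratory values. The SAP gives a liver grouping with n (%), a rate and a listing. The rest of its liver output shows high values by subject, and the product-level plan, which is not available here, may define the areas further. All of this stands as far as it goes.

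Two stronger readings are tempting and should be resisted. A reader might infer that ALT at 12×ULN with normal bilirubin would appear in the report only if someone reported it as an AE. The documents do not support that: the subject is counted in the >5×ULN table and the shift table, and appears in the Grade 3 and liver listings. A reader might also infer that the Possible DILI row or the Hy's Law listing is wrong. Each is labelled as what it is, and neither claims to be the AESI.

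The reply does not remove the gap. AE reporting of a qualifying result is likely but not guaranteed under 5.3.1.1. The Areas of Safety Interest table does not use the hepatic form as a search criterion. Nothing in this SAP says that the product-level plan applies the protocol's definition.

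**Conclusion.** The point holds in a limited form. The protocol's one pre-specified AESI has a laboratory definition and a promised percentage and rate. No SAP output flags, combines and counts the subjects who meet it, and the departure is not declared. What is missing is a label, a count and a rate, not data.

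Severity is minor. The study is descriptive, has about 16 subjects and tests no hypothesis. The documents give no basis for an expected number of cases, and none is assumed. The 25 points for one subject in an arm of four would apply to any single event, so it shows only that classifying one case can move a reported percentage. The conclusion assumes that the SAP text stands as the operative plan and that the product-level plan does not already supply the missing row.

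**What to change.** In SAP 11.2.1 and 11.3.2, add a row *Hepatic injury (protocol 6.1.1.3)*, derived from laboratory data with both protocol limbs exactly as written: same draw for limb 1, and no ALP condition.

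- **Counting rule.** Count each subject once, at the first qualifying post-baseline draw within the treatment-emergent window (to 105 days after the last dose). A rule is needed because the SAP's existing one, a single event per preferred term per subject per day, does not suit a laboratory flag that can recur over repeat draws.
- **Output.** Report n (%), subjects with a first event per 100 patient-years, and a listing, by arm and substudy. State which patient-years form the denominator. The follow-up visit 16 weeks (16×7 = 112 days) after the last dose falls outside the 105-day window, so the listing should show any qualifying draw there and mark it as such.
- **Keep** the Possible DILI search and the Hy's Law listing as separate, labelled outputs.

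If the sponsor prefers the term search as the AESI summary, SAP 14.1 should say so and give the reason.

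The cost is one derived flag, one table row and a listing from data already collected, plus a sentence for the counting rule.

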5.5 Treatments

5.5.1 Treatments Administered

Subjects in each group will receive either 150 mg or 75 mg of risankizumab at Week 0, 4 and every 12 weeks after. All products will be supplied by BI.

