6.1.4 Adverse Event Collection Period

All AEs reported from the time of study drug administration until 16 weeks following discontinuation of study drug administration have elapsed will be collected, whether solicited or spontaneously reported by the subject. In addition, SAEs and protocol-related non-serious adverse events will be collected from the time the subject signed the study-specific informed consent.

Figure 2. Adverse Event Collection

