4.4 Interim Analysis

An interim analysis will be conducted when the last subject completes the Week 28 visit and all data pertaining to Week 28 and earlier are cleaned. For this analysis all Week 16 efficacy endpoints will be analysed, and all safety as well as pharmacokinetic and antiimmunogenicity data received by cut-off date will be analysed. Another interim analysis will be conducted when the last subject completes the Week 52 visit. The analyses will be performed for the efficacy endpoints until Week 52, as well as all safety and pharmacokinetic and immunogenicity data received by cut-off date.

Additional interim analysis may be performed if deemed necessary for regulatory purpose.

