8.0 Patient Disposition

The number of subjects will be tabulated by investigator site and overall. The number of subjects for each of the following categories will be summarized, for overall, two different treatment arms (150 mg or 75 mg) and two diseases (GPP or EP) in the ITT population.

- Number of subjects randomized
- Number of subjects that took at least one dose of study drug
- Number of subjects who completed at Week 28
- Number of subjects who prematurely discontinued from the study before Week 28

In addition, the number and percentage of subject who discontinued the study drug will be summarized by following categorized reason (primary and all) with frequencies and

percentages for overall, two different treatment arms (150 mg or 75 mg) and two diseases (GPP or EP) in the ITT population. Subjects with multiple reasons for premature discontinuation will be counted once in the calculation of the number and percentage of total discontinuations ("Premature Discontinuation").

- Adverse event
- Withdrew consent
- Lost to follow-up
- Others.

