11.2 Analysis of Adverse Events

11.2.1 Treatment-Emergent Adverse Events

Treatment emergent adverse events (TEAEs) are defined as any event with an onset that is after the first dose of risankizumab and with an onset date within 105 days after the last dose of study drug in the analysis period.

- **TEAE of Retreatment:** TEAE are defined as any event with an onset that is after the first dose of retreatment and no more than 105 days after the last dose of study drug.

Events where the onset date is the same as the study drug start date are assumed to be treatment emergent, unless the adverse event start time is prior to the study drug start time. If an incomplete onset date is collected for an adverse event, the event will be assumed to be treatment-emergent unless there is other evidence that confirms that the event is not treatment-emergent (e.g., the event end date is prior to the study drug start date).

The number and percent of subjects experiencing treatment-emergent TEAEs will be tabulated using the Medical Dictionary for Drug Regulatory Activities (MedDRA®) system organ class and preferred term.

Summary tables will be presented as follows:

1. Adverse Event Overview

The number and percentage of subjects experiencing treatment-emergent adverse events will be summarized for the following adverse event categories:

- Any AE
- Any AE that was assessed as related to study drug by the investigator
- Any severe AE
- Any serious AE
- Any serious AE that was assessed as related to study drug by the investigator
- Any AE leading to discontinuation of study drug

- Any AE leading to death
- Any deaths
- Areas of Safety Interest

2. Adverse Events by System Organ Class and Preferred Term

TEAEs will also be summarized and presented using primary Medical Dictionary for Regulatory Activities (MedDRA) system organ classes (SOCs) and preferred terms (PTs). The SOCs will be presented in alphabetical order, and the PTs will be presented in alphabetical order within each SOC.

Subjects reporting more than one adverse event for a given MedDRA preferred term will be counted only once for that term (most severe incident for the severity tables and most related incident for the relationship tables). Subjects reporting more than one type of adverse event within a SOC will be counted only once for that SOC. Subjects reporting more than one type of adverse event will be counted only once in the overall total.

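### Patient-years credit 105 days after the last dose with no cap at data cut-off, so AE rates per 100 patient-years would be too low if produced at the Week 28 and Week 52 interims

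*SAP*

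**What the plan says.** **Denominator.** SAP 11.2.1 (Adverse Event per 100 Patient-Years of Exposure) sums drug exposure "defined as date of last dose – date of first dose + 105 days (5 half-lives)) of all subjects", divides by 365.25 and rounds to one decimal. It is the only rate formula in the SAP.

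**Scope.** The same subsection says: "Adverse events occurring during the entire study will be presented by event rate per 100 patient-year".

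**Numerator.** SAP 11.2.1 counts an event as treatment-emergent if it begins after the first dose and "with an onset date within 105 days after the last dose of study drug in the analysis period". It does not define the analysis period.

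**Interims.** SAP 4.4 plans analyses when the last subject completes Week 28 and again at Week 52. At the first, "all safety as well as pharmacokinetic and antiimmunogenicity data received by cut-off date will be analysed"; the second has an equivalent provision. Protocol 8.1.6 lists, with no entire-study limit, "Summaries (including percentages and event per 100 subject-years) of SAEs, deaths, AEs leading to discontinuation from the study". The disposition table in SAP 8.0 is built on Week 28 ("Number of subjects who completed at Week 28").

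**Timing.** Doses are given "at Week 0, 4 and every 12 weeks after" (Protocol 5.5.1). Adverse events are collected "until 16 weeks following discontinuation of study drug administration have elapsed will be collected" (Protocol 6.1.4).

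**The concern.** The 105 days in the denominator match the 105-day treatment-emergent window, so events and time at risk agree for anyone followed that long after the last dose. They do not agree for a subject still on treatment at a data cut-off: events after the cut-off cannot be counted, yet the time after it is credited.

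The error always runs towards a lower rate, which favours the drug. Its size depends on how fast subjects were recruited and how long after the trigger visit the data were cut, neither of which has anything to do with safety. Rates per patient-year are used mainly for setting beside rates from other data, and an accrual-dependent denominator weakens that comparison for TEAEs, SAEs and areas of safety interest.

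**Working it through.** **Reproducing the 105 days.** 15 weeks × 7 = 105 days, the window in Protocol 8.1.6. Stated as 5 half-lives, it implies 21 days each.

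**Inputs from the documents.** Doses fall at days 0, 28, 112, 196, 280, 364 and every 84 days after, counted from first dose. The interim triggers are day 196 (Week 28) and day 364 (Week 52) of the last subject, and both are dosing visits. There are 16 subjects.

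**Assumed inputs.** The documents give neither the accrual period nor the lag from trigger visit to cut-off. I took evenly spaced accrual over 6 to 36 months (Protocol 8.2 expects recruitment to be difficult), a lag of 0 to 42 days, and no dropout.

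**Formulas, per subject.**
- Credited days = last dose − first dose + 105
- Observed days = min(cut-off, last dose + 105) − first dose
- Understatement of the rate = 1 − (sum observed / sum credited)

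**One continuing subject.** Just after a dose the excess is 105 days; just before the next it is 105 − 84 = 21 days. It cannot reach zero while dosing stays on schedule.

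**Upper limit: all 16 start on one day, no lag.**
- Week 28: 196 + 105 = 301 credited against 196 observed; 105/301 = 35% low.
- Week 52: 364 + 105 = 469 against 364; 105/469 = 22% low.

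Counting both end days changes these to 34.6% and 22.2%.

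**Worked example: 12 months' accrual, no lag.** At the Week 28 cut-off the subjects have between 196 and 561 days on study. Their last doses are at day 196 (4 subjects), 280 (3), 364 (4), 448 (3) and 532 (2).
- Credited: 784 + 840 + 1456 + 1344 + 1064 + 16 × 105 = 7168 days = 19.6 patient-years
- Observed: 16 × (196 + 365.25/2) = 6058 days = 16.6 patient-years
- Understatement: 1 − 6058/7168 = 15.5%. Ten events give 51.0 per 100 patient-years instead of 60.2.

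The Week 52 cut-off adds 168 days, exactly two dosing intervals, to both figures for each subject (16 × 168 = 2688).
- Credited: 9856 days = 27.0 patient-years. Observed: 8746 days = 23.9.
- Understatement: 11.3%. Ten events give 37.0 instead of 41.8.

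**Range over the assumptions (understatement at lag 0 and at lag 42 days).**

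| Accrual | Week 28 | Week 52 |
|---|---|---|
| 6 months | 19.8%, 15.5% | 13.5%, 10.8% |
| 12 months | 15.5%, 12.3% | 11.3%, 9.1% |
| 24 months | 10.5%, 9.8% | 8.3%, 7.9% |
| 36 months | 7.6%, 6.8% | 5.2%, 5.3% |

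A rerun agrees within 0.2 points; the differences come from day-rounding. Lag does not act in one direction, because the excess resets at each dose. With random accrual and each later dose shifted by up to 7 days either way (3000 simulations per cell), the medians run from 7.9% to 18.9% at Week 28 and from 5.8% to 12.7% at Week 52.

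**Sampling error for scale.** Exact Poisson limits for 10 events are 4.80 and 18.39. Divided by 16.6 patient-years, they give 28.9 to 110.8 per 100.

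**Final analysis.** Collection runs 16 × 7 = 112 days after stopping, which covers the 105. An excess arises only for a subject who dies or is lost within 105 days of the last dose. With the last scheduled dose at day 172 × 7 = 1204, a full subject contributes 1309 days. One subject lost right after a dose then lowers the pooled rate by 105/(15 × 1309 + last dose + 105), or 0.50% to 0.53%. Protocol Appendix C puts Week 172 at Day 1162; that figure gives 0.52% to 0.55%.

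**The case against.** **Scope.** The rate subsection is worded for the entire study, and on that scope the formula is sound. No section says that the rate table is produced at an interim: SAP 4.4 does not name rates, Protocol 8.1.6 lists them without tying them to an analysis, and SAP 8.0 concerns disposition. This stands as a reason to keep the finding conditional. It does not remove it: the interims take all safety data, event rates are among the protocol's safety summaries, and the SAP offers no other denominator.

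**A narrower reading.** The treatment-emergent definition refers to the last dose within the analysis period. If at an interim that meant the last dose up to Week 28 or Week 52, early enrollees would carry little or no excess. On the same grid the understatement would be 1.3–10.5% at Week 28 and 0.8–6.8% at Week 52; in the 12-month example, 5.8% and 3.8%. The phrase belongs to the numerator and is absent from the denominator, and it fits poorly with analysing all safety data received by cut-off. Even so, the bias stays downward.

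**What counts as observed.** Non-serious events since a subject's last visit may not be recorded by the cut-off, so time to cut-off may itself slightly overstate observation. This is fair: 16.6 patient-years is time on study up to cut-off. It still removes the time that lies after the cut-off.

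**Consequence.** No test or stopping rule uses these rates. Counts, percentages and listings do not use this denominator, and both arms are affected similarly. All of this stands and sets the rating.

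**Conclusion.** The concern holds, as a minor point. The formula has no cap. If it is applied at an interim, rates for subjects still on treatment are certain to be too low. That it would be applied there is an inference, though a reasonable one.

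The understatement is about 7–20% at Week 28 and 5–14% at Week 52, with limits of 35% and 22% if everyone started together and the data were cut on the trigger visit. These figures rest on assumed accrual, lag and full retention, and on taking the last dose before cut-off; they are not properties of the plan itself. Accrual longer than 36 months would make them smaller. At the final analysis the effect is about half a percent for each subject lost right after a dose. Beside a Poisson interval of roughly 29 to 111 per 100 patient-years, none of this would change a conclusion within the trial.

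**What to change.** In SAP 11.2.1:

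1. State whether rates per 100 patient-years are produced at the Week 28 and Week 52 interims. If they are not, one sentence settles the matter for those analyses.
2. End each subject's time at the earliest of last dose + 105 days; the data cut-off date; date of death; and, only for subjects who have left the study or been lost to follow-up, the date of exit or last contact. Subject time is that end date minus the first dose date, so a fully followed subject keeps exactly the present value.
3. Count treatment-emergent events over the same interval, define the analysis period, and state the cut-off date for each interim.

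Last contact should not be applied to continuing subjects. Taken as the last scheduled visit, it would give 15.4 rather than 16.6 patient-years in the Week 28 example and so would shorten their time. If late recording of non-serious events is a worry, a note to the table can say so.

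The cost is one or two lines of SAP text and programming. Reported interim rates would be somewhat higher, and the final analysis would barely change.
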